6.3. INFORMING SUSTAINABLE SURVEILLANCE

To address this aim, we are proposing to provide consultation and support to the CDC and the NIH for the development of low-cost, sustainable public health surveillance systems for diabetes in children. Based on our experience we know that efficient and complete ascertainment of cases of T2D in youth, and ascertainment of cases of diabetes in older youth present significant challenges. We are proposing two approaches to better understand the underlying systems of care in order to define best practices for case ascertainment. The first builds on data that has been collected over the past 10 years of the SEARCH study as well as data to be collected in SEARCH 3; the second compares data collected by one of the existing six SEARCH centers - a HMO (KPSC) - with analogous data collected by a large integrated multi-payer system (UNC).

6.4. EVALUATING CASE ASCERTAINMENT STRATEGIES: ANALYSIS OF SEARCH REGISTRY DATA

For research question 2.1, we will evaluate (a) whether a longer period of calendar time is required to ascertain cases of youth with T2D or older youth with any type of diabetes than youth with T1D and younger youth; (b) whether any calendar time difference in ascertainment by diabetes type and age can be accounted for by the time from clinical diagnosis to hospitalization or receipt of specialty care services; and (c) if there are temporal changes in observed differences in time to case ascertainment. Date of diagnosis, date of birth, sex, clinical diabetes type, type of health care provider (pediatric endocrinologists, pediatricians, family practice physicians, adult endocrinologists) and the system in which each youth with diabetes received their care (community clinic, university based health system, managed health care organization) around the time of diagnosis are obtained from the medical record, the IPS, or administrative data sources at the time of case validation. Calendar time from date of diagnosis to date of case registration will be calculated in months so that time from diagnosis to registration can be compared by type within each category as well as within type by age category.

Using this information from SEARCH registered cases we will be able to quantify the timing and completeness of case ascertainment under a variety of scenarios. For example, we can simulate specific ascertainment scenarios to compare the completeness of ascertainment of youth with T1D versus T2D by age category if a system relied solely on pediatric endocrinology and hospital-based surveillance networks as compared to if a system that relied on these sources plus primary care providers. We will identify efficient ways to optimize ascertainment of youth with T1D or T2D, using data collected to date by the SEARCH study and through the 2011 incident cohort. This approach goes beyond examining variation by study centers and takes advantage of the diversity within and between the existing SEARCH study centers which conduct ascertainment state-wide (SC, CO), in defined regions (WA, OH), from enrollees in managed health care organizations (CA), and from enrollees in IHS facilities.

6.5. MORTALITY ANALYSIS COMPONENT

Crude mortality rates per 1,000 person-years (p-y) will be calculated, and Poisson and Cox proportional hazards regression analyses will be used to evaluate predictors of mortality (e.g., DM type, race/ethnicity, insurance type). Using the mortality rate of 2.50/1,000 p-y from the Chicago DM registry cohort study ⁽³⁾, we estimate that we will have 117 deaths in the SEARCH cohort. We will calculate the Standardized Mortality Ratio (SMR) comparing the SEARCH cohort to mortality data from the geographic areas from which the SEARCH sample participants are drawn, accounting for the demographic distribution of the cohort with DM.

Reference List

- 1. Writing Group for the SEARCH for Diabetes in Youth Study Group; [name] D, Bell RA, D'Agostino RB, Jr., Imperatore G, Johansen JM, Linder B *et al.* Incidence of diabetes in youth in the United States. *J.A.M.A.* 2007;297:2716-24.

SEARCH Phase 3 Protocol - Section 6B Cohort Study Statistical Considerations Table of Contents

6. ST	TATISTICAL CONSIDERATIONS	1
6.1.	STATISTICAL ANALYTIC METHODS	1
6	1.1. Incidence Rate Estimation	1
6	1.2. Prevalence Estimation	1
6	1.3. Longitudinal Models	1
6	1.4. Mediation Modeling	3
6	1.5. Missing Data Considerations	3
6.2.	POWER ANALYSIS	4
6.2	2.1. Incidence Rate Estimation	4
6.2	2.2. Prevalence Estimation	5
6.2	2.3. Longitudinal Models Component	6
Refe	ERENCE LIST	8

6. Statistical Considerations

There will be four main analytic approaches: 1) estimation of incidence rates of complications (Aims 1 and 2); 2) estimation of prevalence of complications (Aims 1 and 2); 3) longitudinal evaluation of predictors of outcomes and conditions, including consideration of potential mediators and moderators (Aims 1, 2 and 4); and 4) evaluation of mortality rates, including comparison with age-comparable non-diabetic youth (Aim 3). Here we provide selected examples to illustrate analytic strategies and to provide key information regarding sample size and detectable differences.

6.1. STATISTICAL ANALYTIC METHODS

6.1.1. Incidence Rate Estimation

Because all SEARCH Cohort Study participants will have had at least one previous SEARCH in-person visit, we will be able to define a group of participants who were free from the event of interest (i.e., normotensive) at "baseline". Multiple logistic regression methods will be employed to examine the incidence rates of binary measures (e.g., hypertension) of interest. Predictors can include categorical or continuous variables. A continuous variable that measures the time between visits for each participant (to account for the fact that individuals will have different lengths of follow-up) and the predictor- by-time interaction will be included. Next, we will expand the logistic regression model to include other participant level characteristics (e.g., SEARCH clinical center, age, and gender [a "demographically adjusted model"]). We will then expand the model to adjust for other covariates. In addition, we will examine potential interactions; if significant interaction is present, analyses will be performed stratified by that characteristic.

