4.2.1.2. Risk Factors

Glycemic Control. Studies among children and youth with diabetes generally report a constellation of related socio-demographic factors that are associated with poor glycemic control, including race/ethnicity, socioeconomic status, lower parental educational attainment, parental involvement in diabetes management, and family dynamics $^{(81-87)}$. Similar patterns were observed in SEARCH, both for T1 and T2D youth $^{(11)}$, and may be partly mediated by our observation of worse glycemic control among T1D youth on insulin regimens other than CSII $^{(24)}$. In SEARCH, 17% of youth with T1D (n=3947) and 27% of T2D (n=552) respectively had poor glycemic control (HbA_{1c}> 9.5%). For both T1 and T2D, higher A1c was also associated with higher concentrations of apoB and LDL particle size $^{(88)}$, and elevated ACR $^{(68)}$, suggesting possible links early in the history of diabetes between glycemic control and future risk for both macro- and microvascular disease that require further study.

Cardiovascular (CV) Risk Profile. CV risk factors track from childhood to adulthood $^{(89, 90)}$ and risk factors measured in youth predict adult target organ damage $^{(91-93)}$. Thus, an adverse risk profile among youth with diabetes may magnify the already three-fold excess risk for CV mortality associated with diabetes in adulthood $^{(94)}$. In SEARCH, we found that T1 youth had a prevalence of overweight (22%) that was significantly higher than that of non-diabetic counterparts, and ~ 90% of youth with T2D were overweight or obese $^{(95)}$. The prevalence of metabolic syndrome among SEARCH youth with T1D was 14%, and 92% for youth with T2D $^{(96)}$. Further, among youth with T1D, 11% had elevated apoB, 8% had dense LDL, and 12% had elevated LDL-cholesterol. In contrast, among youth with T2D, 36% had elevated apoB, 36% had dense LDL, but only 23% had elevated LDL-cholesterol. Moreover, the prevalence of elevated blood pressure in youth with type 1 was 5.9%; minority ethnic groups, obese adolescents and youth with poor glycemic control were disproportionately affected. In contrast, 23.7% of adolescents with type 2 diabetes had elevated BP (p<0.0001) $^{(97)}$.

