5.1.7. Nephropathy

Microalbuminuria has been the mainstay of diabetic nephropathy prediction modeling. However, recently its validity and robustness has been questioned ⁽¹³⁾, with increasing recognition of non-proteinuric diabetic kidney disease ^(14, 15), the tendency of microalbuminuria to regress more often than progress, and about 1/3rd of microalbuminuric patients never progressing to proteinuria ^(16, 17). Nonetheless, patients who develop persistent microalbuminuria have about 5 times the risk of progressing to overt nephropathy compared to those who are normoalbuminuric at a baseline observation at least 5 years after diabetes diagnosis ⁽¹⁸⁾. The first two phases of SEARCH collected random urine samples. The pitfalls of random urines, especially in adolescents who are susceptible to benign orthostatic proteinuria (frequency of 2-5%), are well appreciated. However, for the SEARCH Cohorts Study, we will continue to collect a random urine sample during the visit for longitudinal analysis. Unique to SEARCH 3, we will add a first morning void sample that the participant will bring to the clinic. Urinary albumin and creatinine will be measures to obtain an albumin/creatinine ratio. Samples will not be collected during the visit on participants who are pregnant or menstruating, have had a fever greater than 100 degrees in the past 24 hours, or who have taken an antibiotic in the past seven days for a urinary tract infection. A dipstick test will also be performed to test for the presence of blood or leukocytes. Urine will also be stored (first morning void only) to assess other markers of nephropathy in the future. (08/2011)

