The initial model will examine outcomes (measured previously between 1 (baseline) and 4 times (baseline, 12, 24, 60 mo visits) and once during the SEARCH Cohort Study visit), the predictor of interest (e.g., DM type), the duration of diabetes at each measurement time and the predictor-by-diabetes duration interaction. These models will then be expanded to include demographic information (e.g., sex) that would be considered as fixed/non-time varying effects. In addition, based on our experience with performing these longitudinal analyses on the SEARCH 2 cohort, we also propose to consider treating the exposure (predictor) of interest as a time-varying covariate in these models as well. This will allow the time-varying correlation of the predictor to the outcome of interest to be modeled correctly. We will also consider adding other timevarying covariates (e.g., BMI z-score) into these models as needed to examine the specific relationships being studied. These mixed effects models also are flexible to allow for potentially non-linear relationships to be modeled over time, and permit random rates of progression, consistent with a perspective that different participants progress through time at different rates. Use of random intercepts and/or slopes provides a source of autocorrelation between repeated measures. More flexible structures for the correlation between repeated measures will be investigated using combination mixed models that allow the specification of separate parameters representing variation between experimental units, and serial correlation within units. Our choice of methods for accounting for serial correlation depends on the plausibility of the model, and the number of outcomes relative to the number of participants. For example, with many participants and few repeated measurements, an unstructured covariance matrix can often provide for the most efficient estimation of model parameters.

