6.2.1. Incidence Rate Estimation

To estimate power for this component we first had to estimate the proportion of participants who would be free of the condition at their initial in-person visit during SEARCH 1 and 2. Table 6-1 shows the expected sample sizes available for comparing incidence rates between subgroups under two scenarios: 1) proportion in subgroups are 86% versus 14% (the proportions of T1D and T2D), and 2) proportion in subgroups are 65% versus 35% (the proportions of NHW and all others).

 Table 6-1: Expected Sample Sizes Available for Comparing Incidence Rates between Subgroups

 Under Two scenarios

	Scenario 1		Scena	ario 2		
Outcome (% of participants free of	Subgroup A	Subgroup B	Subgroup A	Subgroup B		
condition at initial SEARCH visit)	(86%)	(14%)	(65%)	(35%)		
	Expected n	Expected number of participants free of outcome at initial visit				
Hypertension (92%)	2504	423	1893	1019		
Obese (bmi-z \ge 95 th %ile) (76%)	2069	349	1564	842		
High LDL (≥ 100) (57%)	1511	262	1173	631		
High ACR (≥30 (90%)	2450	414	1852	997		
Hypoglycemia in last 6 months (91%)	2477	418	1872	1008		
DKA in last 6 months (85%)	2314	391	1749	941		

Using this table we can determine detectable differences for each outcome/group comparison for a variety of plausible scenarios for incidence rates. Table 6-2 illustrates detectable differences assuming a two group continuity corrected chi-square test for a variety of scenarios with alpha=0.05 (2-sided).

Table 6-2. Detectable Differences in Selected Outcomes Assuming a Two-Group Continuity							
Corrected Chi-square Test for a Variety of Scenarios with Alpha=0.05 (2-sided)							
	Scenario 1: Example T1 vs. T2 Scenario 2: NHW vs. Other						
Outcome	Incidence Rate	Detectable Rate	Incidence Rate	Detectable Rate			
	for T1	for T2 (Power)	for NHW	for Other			
				Race/Ethnic			
				Group (Power)			
Hypertension	6%**	10% (80%)	6%**	10% (96%)			
	12%	18% (88%)	12%	17% (95%)			
Obese	5%	10% (90%)	9%	14% (95%)			
	10%	16% (86%)	19%	25% (91%)			
High LDL	23%	32% (84%)	14%	20% (89%)			

Section 6B - Statistical Considerations (P	hase 3 - 12/2010)
Cohort Study	

	33%	43% (85%)	24%	31% (87%)	
High ACR	9%	15% (93%)	5%	8% (86%)	
	19%	26% (87%)	10%	14% (87%)	
Hypoglycemia in last 6 months	11%	17% (90%)	23%	28% (82%)	
	21%	28% (86%)	33%	39% (88%)	
DKA in last 6 months	15%	21% (81%)	9%	13% (87%)	
	25%	32% (80%)	19%	24% (84%)	

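### Section 6.1.1 counts incident hypertension, high LDL and high ACR from status below then above a cut-off, with no allowance for within-person fluctuation, so part of a T1D–T2D incidence difference could be artefact

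*Protocol*

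**What the plan says.** Section 6.1.1 forms the at-risk group from an earlier SEARCH visit: "we will be able to define a group of participants who were free from the event of interest (i.e., normotensive"). The later outcome is binary: "Multiple logistic regression methods will be employed to examine the incidence rates of binary measures (e.g., hypertension) of interest". Time between visits and its interaction with the predictor enter the model.

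Table 6-1 (Section 6.2.1) counts those "Expected number of participants free of outcome at initial visit". It puts 92% free of hypertension (no cut-off given), 57% free of LDL ≥100 and 90% free of ACR ≥30. Table 6-2 powers the T1D–T2D and race/ethnicity contrasts on these groups.

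Section 6.1.3 has outcomes measured at one to four earlier visits and "once during the SEARCH Cohort Study visit". It plans mixed models for the continuous outcomes.

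On albuminuria, Section 5.1.7 notes "the tendency of microalbuminuria to regress more often than progress" and the pitfalls of random urine, then says "we will continue to collect a random urine sample during the visit for longitudinal analysis". A first morning void is added, without a stated role in defining an incident case.

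**The concern.** If people are selected because one reading was low, some will read high later even when their usual level has not moved. The rate of such crossings depends on how near the group's distribution lies to the cut-off. A group with higher baseline prevalence has more people just below the line and so more crossings.

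T2D has the higher prevalence of both elevated blood pressure and elevated ACR in this protocol. Research Question 1.1 asks whether incidence differs by diabetes type. Section 6.1.1 could answer yes without any excess progression in T2D, and it names no companion result that would reveal this. For ACR, Section 5.1.7 itself describes the instability.

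**Working it through.** **1. Reproduce the plan's power.** Two-group test with continuity correction, two-sided alpha 0.05, pooled variance under the null, Table 6-1 sizes for T1D/T2D:

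| Outcome | Rates | n | Table 6-2 | Recomputed |
|---|---|---|---|---|
| Hypertension | 6% vs 10% | 2504/423 | 80% | 80.3% |
| High LDL | 23% vs 32% | 1511/262 | 84% | 84.7% |
| High ACR | 9% vs 15% | 2450/414 | 93% | 93.2% |

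**2. No-change model.** Baseline and follow-up values are bivariate normal with correlation r and the same distribution at both visits. With prevalence p, the cut-off is c = Φ⁻¹(1 − p), and

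P(above later | below at baseline) = [p − P(both above)] / (1 − p).

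Inputs by type:
- Elevated blood pressure: 5.9% in T1D and 23.7% in T2D (Section 4.2.1.2, Risk Factors).
- Elevated ACR: 9.2% and 22.2% (Diabetic Nephropathy text of Section 4B).
- r = .50, .65, .75, .86 (Table 6-4, stated for systolic pressure, BMI z-score and LDL). Using them for ACR is an assumption, and r = .90 and .95 are added assumptions.

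Example, blood pressure at r = .50. In T1D, P(both above) = 1.54%, so (5.9 − 1.54)/94.1 = 4.6%. In T2D it is 11.13%, so (23.7 − 11.13)/76.3 = 16.5%.

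**3. Results.** The last columns put the no-change rates through the test of step 1 at Table 6-1 sizes.

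| r | BP T1D | BP T2D | P(significant) | ACR T1D | ACR T2D | P(significant) |
|---|---|---|---|---|---|---|
| .50 | 4.6% | 16.5% | >99% | 7.0% | 15.5% | 99.9% |
| .65 | 4.0% | 13.7% | >99% | 5.9% | 12.9% | 99.3% |
| .75 | 3.4% | 11.5% | >99% | 5.0% | 10.9% | 97.9% |
| .86 | 2.6% | 8.6% | 99.8% | 3.8% | 8.1% | 92.7% |
| .90 | 2.2% | 7.2% | 99.3% | 3.2% | 6.8% | 87.9% |
| .95 | 1.6% | 5.1% | 96.1% | 2.3% | 4.8% | 74.8% |

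Table 6-1 applies one pooled share to both types. Rescaling to the type-specific shares cuts the T2D groups to 423 × 0.763/0.92 ≈ 351 and 414 × 0.778/0.90 ≈ 358. The probabilities at .95 then become 94% (BP) and 70% (ACR).

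**4. Pooled rates beside the plan.** With the Table 6-1 prevalences (8%, 43%, 10%) and r from .50 to .86, no-change crossings are 6.1–3.4% for hypertension, 28.7–14.7% for LDL and 7.5–4.1% for ACR.

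**5. What a confirming reading does.** Suppose a second follow-up reading with independent error must also exceed the cut-off. The no-change ACR rates fall to 1.7% vs 5.3% at r = .50 and 1.4% vs 3.5% at .86. The gap shrinks but stays.

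**6. What net change does.** When the distribution is unchanged, the share of a group moving up and the share moving down both equal p − P(both above). In the T1D example each is 5.9 − 1.54 = 4.4% of the group, so net change is zero.

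**The case against.** The strongest reply is that the protocol never writes out an incident-case rule. Counting one later reading over the same cut-off is the natural reading of 6.1.1, but no sentence says so. The hypertension cut-off and the number of pressure readings are not given, Section 6 calls its content selected examples, and a SAP could add a rule. This stands against any claim that the protocol mandates a single-reading definition. The at-risk selection, the ACR and LDL cut-offs, the single Cohort visit and the powered contrast are nonetheless set in this document.

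Second, the plan already has mitigation: mixed models for continuous outcomes, a first morning void, exclusions for urine collection and a dipstick test. Keeping the random sample has a good reason, since Phases 1 and 2 collected random urine. All true, but nothing ties an incidence claim to these results.

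Third, the Table 6-4 correlations span years and include real change, so the model overstates pure noise. That also stands. No test-retest figure appears in the protocol.

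Three stronger readings are tempting and are not supported:
- A reader might infer that fluctuation alone produces the planned incidence. The pooled figures in step 4 look close, but by type the T1D no-change rates (BP 2.6–4.6%, ACR 3.8–7.0%) stay below the planned 6% and 9% at every correlation in Table 6-4.
- A reader might extend the false contrast to LDL. The protocol gives no prevalence of LDL ≥100 by type, so it cannot be computed.
- A reader might set the 2–5% orthostatic proteinuria against the planned 5% ACR incidence. That compares a prevalence with an incidence. People whose baseline random ACR was raised for this reason have already left the at-risk group.

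**Conclusion.** The concern holds in limited form. As written, Section 6.1.1 can mistake fluctuation for differential progression, so part of any T1D–T2D difference in incident hypertension or albuminuria could be artefact. With unchanged distributions, the apparent gap over the Table 6-4 correlations is about 6 to 12 percentage points for blood pressure and 4.3 to 8.5 for ACR. The gaps that Table 6-2 plans for are 4 and 6 points. Even at an assumed correlation of .95, the planned test would probably call the gap significant (step 3).

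This rests on a bivariate-normal model, on prevalences from Section 4B whose definitions may differ from those of Table 6-1, on correlations that mix noise with real change, and on borrowing them for ACR. It shows that the design is exposed. It does not measure how much of an observed difference would be spurious.

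**What to change.** In Section 6.1.1:

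(a) Report incident albuminuria on the random ACR, for comparability with Phases 1 and 2, and also as confirmed by a first-morning-void ACR ≥30 at the Cohort visit. Both are needed: baseline had random urine only, so the confirmed definition is stricter at follow-up than at entry.

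(b) For hypertension, LDL and ACR, report reverse transitions (above to below) and net change by group. Confirmation alone does not remove the T1D–T2D gap; net change does so in the no-change model.

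(c) Claim differential progression in blood pressure or LDL by type or race/ethnicity only where the continuous mixed model of 6.1.3 agrees. Its predictor-by-duration interaction has no expected difference when neither group changes.

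I would not add a minimum-rise rule, because the documents give no within-person variability on which to set one. Nor would I require two consecutive visits, which could apply only to the 2002–2005 cases with follow-up visits.

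The cost is wording and extra tables from data already collected. Confirmed ACR incidence will be lower, and Table 6-2 needs a row for that definition with less favourable detectable differences.

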6.1.2. Prevalence Estimation

Some of the outcomes of interest will not have been measured during SEARCH 1 or 2, such as outcomes including retinopathy and neuropathy. Therefore, prevalence of these outcomes will be estimated. Models to evaluate cross-sectional associations of risk factors will use logistic regression and will proceed as described above to account for potential confounding or effect modification.

6.1.3. Longitudinal Models

All participants in the SEARCH Cohort Study will have already had at least one inperson visit during SEARCH 1 and 2, and ~75% of the 2002-2005 incidence cases have at least 2 in-person visits per the SEARCH 2 protocol. Since SEARCH 2 also included longitudinal data (there are over 2000 SEARCH participants already with at least one follow-up visit), our team developed a plan for modeling longitudinal data. Specifically, we will use longitudinal mixed effects analysis of covariance models that always include duration of diabetes as a time-varying covariate. This approach correctly models the varying durations of disease prior to the initial SEARCH in-person visit, and the varying

Section 6B - Statistical Considerations (Phase 3 - 12/2010) Cohort Study

durations of time allowed via the SEARCH data collection windows between the initial and subsequent visits.

The initial model will examine outcomes (measured previously between 1 (baseline) and 4 times (baseline, 12, 24, 60 mo visits) and once during the SEARCH Cohort Study visit), the predictor of interest (e.g., DM type), the duration of diabetes at each measurement time and the predictor-by-diabetes duration interaction. These models will then be expanded to include demographic information (e.g., sex) that would be considered as fixed/non-time varying effects. In addition, based on our experience with performing these longitudinal analyses on the SEARCH 2 cohort, we also propose to consider treating the exposure (predictor) of interest as a time-varying covariate in these models as well. This will allow the time-varying correlation of the predictor to the outcome of interest to be modeled correctly. We will also consider adding other timevarying covariates (e.g., BMI z-score) into these models as needed to examine the specific relationships being studied. These mixed effects models also are flexible to allow for potentially non-linear relationships to be modeled over time, and permit random rates of progression, consistent with a perspective that different participants progress through time at different rates. Use of random intercepts and/or slopes provides a source of autocorrelation between repeated measures. More flexible structures for the correlation between repeated measures will be investigated using combination mixed models that allow the specification of separate parameters representing variation between experimental units, and serial correlation within units. Our choice of methods for accounting for serial correlation depends on the plausibility of the model, and the number of outcomes relative to the number of participants. For example, with many participants and few repeated measurements, an unstructured covariance matrix can often provide for the most efficient estimation of model parameters.

For analysis of longitudinal discrete outcomes (e.g. transfer of care from a pediatric to adult provider), we will use the generalized estimating equation (GEE) approach to fit logistic or log-linear models that account for the dependency between repeated measures. GEE techniques allow estimation of model parameters and their standard errors from longitudinal data having continuous and categorical responses and potentially missing observations. An advantage of this technique is that the assumptions required are weaker than those of maximum likelihood techniques: one need not specify the distribution of the dependent variable, just the relationships between the marginal mean and variance, and between the marginal mean and covariates.

